### **10.1.2. Other Safety Topics of Interest**

The following summaries of TEAEs associated with safety topics of interest will include incidence of TEAEs, treatment-related TEAEs, and serious TEAEs by PT and will be prepared separately for TEAEs on study and on treatment. All Sponsor-defined terms will be identified prior to database lock for the primary analysis and will be included in the CSR.

- Cardiovascular system-associated TEAEs comprised of terms in the Cardiac SOC, Vascular SOC, and Cardiac Arrhythmias Standardized MedDRA Query (SMQ). Separate summaries of terms in the Cardiac Arrhythmias SMQ will also be prepared.
- Hypotension-associated TEAEs comprised of Sponsor-defined terms
- Hepatic-associated TEAEs comprised of terms in the Hepatic Disorders SMQ, excluding the following sub-SMQs: alcohol related, congenital, familial, neonatal, and genetic disorders of the liver; liver infections; and pregnancy-related hepatic disorders
- Pancreatic-associated TEAEs comprised of terms in the Acute Pancreatitis SMQ
- Fluid retention-associated TEAEs comprised of terms in the haemodynamic oedema, effusions, and fluid overload SMQ
- Anemia-associated TEAEs comprised of Sponsor-defined terms
- Hyperkalemia-associated TEAEs comprised of PTs “Hyperkalemia,” “Hyperkalaemia,” and “Blood potassium increased”

### **10.1.3. On-Treatment Summaries**

Select summaries for TEAEs while on-treatment will additionally be prepared. On-treatment will be defined as TEAEs starting  $\leq 30$  days from date of last dose in randomized treatment period for patients who discontinue treatment or any TEAE prior to first dose in OLE for patients who complete the randomized treatment period. Summaries will be prepared for TEAEs associated with safety topics of interest in Section 10.1.2. Patient incidence of on-treatment TEAEs and the total number of entries by PT will also be provided.

### **10.1.4. Adverse Events During OLE**

At the primary analysis, summaries of AEs with onset on or after first dose of sparsentan in the OLE will be presented for the OLE FAS by randomized treatment group and overall. Time to event analyses will not be performed due to the anticipated small sample size.

## 10.2. Extent of Exposure and Compliance

The following extent of exposure parameters will be summarized both continuously using descriptive statistics and categorically using counts and percentages by treatment group and overall:

- Duration of treatment (weeks)
- Duration of treatment with initial/reduced dose (weeks)
- Duration of treatment with target dose (weeks)
- Time to titration to target dose (weeks)
- Total duration of study medication interruptions (days)

Duration of treatment (weeks) will be calculated as follows:

- Duration of treatment = (Date of last dose of study medication – Date of first dose of study medication + 1) / 7

Duration of treatment with initial/reduced dose and duration of treatment with target dose will be calculated similarly. For patients who received the target dose on Day 1, the duration of treatment with initial/reduced dose will be set to 0 weeks.

For patients who titrated to the target dose, the time to titration to target dose (weeks) will be calculated as follows:

- Time to titration to target dose = (Date of first dose of target dose – Date of first dose of study medication + 1) / 7

The duration of each incidence of study medication interruption will be calculated as follows:

- Duration of study medication interruption = (Date of restart of study medication – Date of temporary discontinuation)

The total duration of study medication interruptions is the sum of duration of study medication interruption over each incidence of interruption. For patients with no study medication interruption, the total duration is considered 0 days.

A summary of patients who had the following dose modifications will be summarized by frequency count and percentages:

- Titration to target dose
- Dose reductions after titration to target dose

Patient's compliance rate (%) with study medication during the treatment period will be calculated as follows at the final analysis:

- $100 \times \left\{ \frac{\text{Total number of capsules dispensed} - \text{Total number of capsules returned}}{\text{Expected number of capsules to be taken based on the patient's titration schedule}} \right\}$

Compliance rates will be summarized both continuously using descriptive statistics and categorically using counts and percentages by treatment group and overall.

Compliance will also be derived from the dose log to supplement the assessment using drug dispensation and return. Compliance based on the dose log for each patient will be determined as follows:

- Total number of capsules taken = sum over all actual dose intervals, where an actual dose interval is defined as any dose log record where actual dose >0 capsules and derived as number of days × number of capsules
- Total number of capsules missed = sum over all missed dose intervals defined as any record where dose = 0 capsules and CRF indicates missed dose; derived as number of days × number of expected capsules
- Total number of capsules taken over prescribed dose = sum of all dose intervals where dose log indicates overdose and derived as number of days × number of capsules
- Dose log compliance =  $100 \times \{(\text{Total number of capsules taken}) / (\text{Total number of capsules taken} + \text{Total number of capsules missed} - \text{Total number of capsules taken over prescribed dose})\}$

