### **7.3. Protocol Deviations**

Protocol deviations for missed visits, missed assessments, out-of-window visits or assessments, and violations of inclusion/exclusion criteria (where possible) will be determined based on available data. All other protocol deviations will be collected by the clinical research associates.

Protocol deviations that could potentially affect the efficacy or safety conclusions of the study will be identified, and the assessment of determination of evaluable patients for analysis populations (PPPA, PPFA and PK Analysis Set) will be performed and approved by the Study Statistician, Medical Monitor, and Clinical Study Manager prior to database lock and unblinding of individual patient treatment information.

Evaluability of patients will be based on the following:

- Compliance of study entry criteria (inclusion and exclusion)
- Correct stratification at randomization
- Received the randomized treatment
- Adequate study medication exposure (no extended dosing interruptions)
- Adequate treatment compliance based on prescribed dose level (within 80% to 120%)
- No prohibited concomitant medications or therapies during the study
- No accidental or intentional unblinding at the investigational site

- No other major protocol deviations that may affect efficacy or safety conclusions, may include the following:
  - Non-withdrawal although at least 1 withdrawal criterion was met
  - Extensive visit window violations
  - Extensive missing visits
  - Nonadherence to study procedures
  - Inadequate handling of study medication

Major protocol deviations will be summarized by deviation category (overall and due to coronavirus disease 2019 [COVID-19]) and presented in a by-patient data listing.

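### The dose-log compliance formula in SAP 10.2 overstates compliance: it cannot see days on part of the prescribed dose, and its overdose term is defined in two conflicting ways

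*SAP*

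**What the plan says.** SAP 10.2 gives two compliance rates for the double-blind period. The main one, also in Protocol 12.6, is capsules dispensed minus capsules returned, divided by the number expected under the patient's titration schedule; SAP 10.2 specifies it for the final analysis. The second is introduced with "Compliance will also be derived from the dose log to supplement the assessment using drug dispensation and return". It is 100 × *taken* / (*taken* + *missed* − *over*), with these terms:

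- *Taken*: "sum over all actual dose intervals, where an actual dose interval is defined as any dose log record where actual dose >0 capsules", counted as days times capsules.
- *Missed*: "sum over all missed dose intervals defined as any record where dose = 0 capsules and CRF indicates missed dose". Each such record contributes its expected capsules per day multiplied by its days.
- *Over*: named as capsules taken above the prescribed dose, but defined as the "sum of all dose intervals where dose log indicates overdose and derived as number of days × number of capsules".

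Protocol 8.8 defines compliance as capsules actually taken relative to those that should have been taken. SAP 7.3 makes compliance between 80% and 120% at the prescribed dose level one of the evaluability criteria for the Per Protocol sets (PPPA at the primary analysis, PPFA at the final analysis). It does not say which of the two rates is meant.

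**The concern.** The denominator should equal the capsules prescribed. As written it departs from that in two places.

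First, *missed* is confined to records with a dose of zero. At the target dose of two capsules (SAP 4.2.1), the only possible partial dose is one capsule. Such a day adds one to the numerator, one to the denominator, and nothing to *missed*, so the capsule not taken disappears.

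Second, the *over* term has a label that points to the excess above prescription and a derivation that does not. The derivation uses the same count as *taken* (days times capsules), whereas the *missed* term refers explicitly to expected capsules. A programmer who follows the derivation subtracts every capsule taken on an overdose record, including those that were prescribed.

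At stake are the accuracy of the reported compliance table and, if this rate is the one used, who falls inside the 80–120% limits.

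**Working it through.** The documents give no worked compliance value, so there is no figure to reproduce. I applied the formula to illustrative 100-day logs with two capsules prescribed per day and compared it with Protocol 8.8 compliance, *taken* / 200. The examples assume that the log records the capsules actually taken. As a check, full dosing gives 200/200 = 100%.

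**Doses below prescription** (the overdose term plays no part)

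- One of two capsules every day: *taken* 100, *missed* 0. Formula 100/100 = 100%; true 100/200 = 50%.
- A share p of days at one of two capsules: *taken* = 200 − 100p, and the denominator is the same, so the score is always 100%. True compliance is 100 × (200 − 100p)/200 = 100 × (1 − p/2)%, which is below 80% once p > 0.40. At p = 0.60 it is 70%.
- Half the capsules, by skipping 50 whole days: *taken* 100, *missed* 50 × 2 = 100. Formula 100/200 = 50%, correct.
- Half the capsules, mixed (25 days skipped, 50 days at one of two, 25 full): *taken* 50 + 50 = 100, *missed* 25 × 2 = 50. Formula 100/150 = 66.7%; true 50%.
- Reduction to one capsule as prescribed, and taken: 100/100 = 100%, correct.

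**Doses above prescription**

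Three capsules for two on 20 of 100 days: *taken* = 80 × 2 + 20 × 3 = 220.

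- Literal derivation: *over* = 20 × 3 = 60; 220/(220 − 60) = 137.5%.
- Excess only: *over* = 20 × 1 = 20; 220/(220 − 20) = 110%, which equals the true 220/200.

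With x such days the literal score is (200 + x)/(200 − 2x). It passes 120% when 3.4x > 40, that is x > 11.8. At 12 days it is 212/176 = 120.5%, against a true 212/200 = 106%. If every record is an overdose and none is missed, the literal denominator is zero.

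Overdose days can also mask missed days. With 40 days missed, 15 days at four for two and 45 full days, *taken* = 60 + 90 = 150, *missed* = 80, and literal *over* = 60. Formula 150/170 = 88.2%; true 150/200 = 75%. Counting only the excess, *over* = 30, and 150/200 = 75%.

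**The case against.** The strongest reply is that little depends on this rate. It is supplementary. The capsule-count rate has the expected number of capsules as its denominator, so it has neither fault and would show one-of-two dosing as 50%. The Per Protocol analyses are supportive (Protocol 12.7; SAP 8.1, 8.5.2, 8.6.3), and SAP 7.3 decides evaluability on several criteria, approved before unblinding. All of this stands. One qualification is that SAP 10.2 ties the capsule-count rate to the final analysis and puts no such limit on the dose-log rate, so the reply is weaker for PPPA than for PPFA.

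On the overdose term, the reply is that the label settles the meaning: "Total number of capsules taken over prescribed dose = sum of all dose intervals where dose log indicates overdose" names an excess, and read so the formula is right. That is fair, and this part is a conflict to resolve rather than a certain error. It does not touch the partial-dose fault, which is present on either reading.

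The documents give no frequency for partial dosing or overdosing and do not show how the log captures a partial dose. Protocol 8.2.3 tells patients not to take two doses in a day. The logs above therefore show how the formula behaves, not how large the error will be in the trial.

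Two stronger readings are tempting. A reader might infer that anyone who takes half the capsules scores 100%; whole-day misses are in fact scored correctly. A reader might also infer errors in both directions, because both limits are involved. Both faults raise the score: one can hide true values below 80%, and the other can push true values of about 106–110% above 120%.

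**Conclusion.** The formula overstates compliance. The partial-dose fault follows from the text on any reading: 100% is reported where 50% is true at the extreme, and a fall below 80% is hidden once more than 40% of days are at one of two capsules, provided the log holds actual capsule counts. The overdose fault holds only under the literal derivation (137.5% against 110% in the example) and vanishes if only the excess is subtracted; the SAP has to say which.

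It would go too far to conclude that the Per Protocol sets are compromised. Membership is affected only if the dose-log rate is the one held to the 80–120% limits, and SAP 7.3 leaves that open. The primary and key secondary analyses on the PAS and FAS do not use compliance and are unaffected. This is a correction worth making to a stated derivation, not a threat to the confirmatory results.

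**What to change.** Set dose-log compliance to 100 × capsules taken / sum over dose-log intervals of (days × prescribed capsules), leaving out interruptions directed by the Investigator.

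If the present layout is kept, define *missed* as days × (prescribed − taken) on every record below prescription, again leaving out directed interruptions, and *over* as days × (taken − prescribed) on every record above it. *Taken* + *missed* − *over* then equals the prescribed number on each record, and the examples return 50% and 110%.

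In SAP 7.3, state which compliance rate is held to the 80–120% limits at the primary analysis and which at the final analysis.

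The cost is one formula and one sentence in the SAP and one derivation in programming. No new data are needed if, as the formula presupposes, the log holds actual and prescribed capsules.

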### 10.3. Prior and New Concomitant Medications and Procedures

Prior and concomitant medications and procedures will be collected from 3 months prior to Screening through the patient's final study visit. In addition, a comprehensive history of medications previously used for treatment of IgAN, including systemic corticosteroids or other systemic immunotherapeutic agents, will be collected. For medications, verbatim terms on eCRFs will be mapped to Anatomical Therapeutic Chemical (ATC) class and preferred name using the World Health Organization (WHO) Drug Dictionary Enhanced. For procedures, verbatim terms will be mapped to PTs and SOC using MedDRA.

Pretreatment medications are those medications with start and stop dates prior to the initial dose of study medication. Prior concomitant medications are those medications started prior to and continued after the initial dose of study medication. New concomitant medications are those medications that were started on or after the initial dose of study medication. If it cannot be determined whether the medication was a new concomitant medication due to a partial start or stop date or if the medication is taken on the same date as the initial dose of study medication, then it will be counted as a new concomitant medication.

Similarly, prior procedures are those procedures with a start date prior to initial dose of study medication. Concomitant procedures are those procedures that were started after the initial dose of study medication.

Select pretreatment medications, including ACEIs, aldosterone blockers, aliskiren, ARBs, corticosteroids, immunosuppressive medications, diuretics, and all antihypertensives, will be summarized for each treatment group by WHO ATC level 2, WHO ATC level 4, and preferred name. All other pretreatment medications will be listed only.

Prior and new concomitant medications will be summarized separately for each treatment group by WHO ATC level 2, WHO ATC level 4, and preferred name. These summaries will present the number and percentage of patients using each medication. Patients may have more than one medication per ATC level and preferred name. At each level of patient summarization, a patient

is counted once if he/she reported one or more medications at that level. Each summary will be ordered by descending order of incidence of ATC level and preferred name within each ATC level.

Prior and concomitant procedures will be summarized for each treatment group by SOC and PT.

## **10.4. Clinical Laboratory Evaluations**

Laboratory parameters will be summarized in the standard international system of units. Quantitative laboratory results will be summarized by treatment group using descriptive statistics at baseline and each post-baseline scheduled visit. Both absolute and percentage change from baseline will also be summarized.

### **10.4.1. Shifts in Normal Range**

Shift tables (ie, low-normal-high at baseline versus low-normal-high at post-baseline visit in a 3-by-3 contingency table) from baseline to worst (including scheduled or unscheduled) and last value (scheduled or unscheduled) will be provided for hematology, serum chemistry, coagulation, quantitative urinalysis, and lipids by treatment group. For urinalysis parameters, a shift table depicting shifts to/from positive/negative from baseline to worst and last value will be provided.

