### **8.3.3. Treatment in Follow-up Period**

Following the 110-week blinded treatment period, treatment with study medication will be discontinued for 4 weeks. At this time, the Investigator should resume standard-of-care treatment, including RAAS inhibitor treatment. Where possible, the same treatment regimen the patient was on at study entry (ie, the same ACEI and/or ARB at the same dose[s]) should be used, unless in the Investigator's opinion, an alternative treatment approach is warranted. The Investigator may make additional adjustments in anti-hypertensive medications if considered necessary to adequately control blood pressure. Patients will return to the site for the Week 114 visit after study medication has been discontinued.

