## 10. SAFETY AND TOLERABILITY

Safety analyses will be conducted using the Safety Analysis Set at both the primary and final analysis. At the primary analysis, all available data will be summarized. Unless otherwise noted, all safety analyses will be conducted using on-study data. All safety analyses specified below refer to the double-blind period only, except where noted. If >5% of patients initiate RRT while on study, select summaries excluding results after initiation of RRT may be prepared.

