### **10.4.2. Shifts in CTCAE Toxicity Grade**

Shifts in Common Terminology Criteria for Adverse Events (CTCAE) toxicity grade of laboratory tests from baseline to worst value (scheduled or unscheduled), last value (scheduled or unscheduled), and at each scheduled post-baseline visit will be provided by treatment group. The toxicity grades are in the CTCAE version 4.03.

Summaries will present the number and percentage of patients with shifts in laboratory toxicity grade by treatment group.

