### **10.6.1. Peripheral Edema**

The presence and staging of peripheral edema will be summarized by frequency counts and percentages based on the following grades: 0, 1+ (trace), 2+ (mild), 3+ (moderate), and 4+ (severe), where 0 denotes no presence of edema. A shift table indicating changes in edema severity from baseline to worst (including scheduled and unscheduled), last value (scheduled and unscheduled), and at each scheduled post-baseline visit will be provided by treatment group.

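### In the normal-range laboratory shift tables (SAP 10.4.1), the last value at the final analysis is a post-treatment reading for patients who attend Week 114

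*SAP*

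**What the plan says.** SAP 10 sets the data scope for safety: "Unless otherwise noted, all safety analyses will be conducted using on-study data". It adds: "All safety analyses specified below refer to the double-blind period only, except where noted".

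Within that scope, SAP 10.4.1 plans normal-range shift tables "from baseline to worst (including scheduled or unscheduled) and last value (scheduled or unscheduled) will be provided for hematology". The same rule covers lipids, coagulation, chemistry and the quantitative urine measures. A positive/negative shift table for urinalysis uses the same two endpoints, worst and last. Nothing in 10.4.1 limits either endpoint to time on treatment.

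Two neighbouring sections go further. CTCAE-grade shifts (SAP 10.4.2) cover the worst value, "last value (scheduled or unscheduled), and at each scheduled post-baseline visit will be provided by treatment group". Edema shifts (SAP 10.6.1) likewise cover "last value (scheduled and unscheduled), and at each scheduled post-baseline visit will be provided by treatment group". SAP 10.4 also has quantitative laboratory results "summarized by treatment group using descriptive statistics at baseline and each post-baseline scheduled visit".

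Protocol 8.3.3 has study medication stopped for four weeks after Week 110. It continues: "At this time, the Investigator should resume standard-of-care treatment, including RAAS inhibitor treatment". Protocol Table 15.1-2 schedules Panel A laboratories, the lipid panel, the 24-hour urine collection and the edema assessment at Week 114.

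**The concern.** A baseline-to-last shift table presented by treatment group is commonly read as showing where patients stood at the end of treatment. Here the last on-study reading of a patient who completes follow-up comes after the randomized comparison has been withdrawn. Both arms are by then expected to be back on standard ACEI or ARB therapy. For irbesartan patients that is close to the same class of drug. For sparsentan patients it removes the endothelin-receptor component that distinguishes the arms.

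Nothing in the table title or definition tells the reader this. In 10.4.1 the only companion is the worst value, which is also taken from all on-study data. That section therefore contains no shift restricted to on-treatment readings, and no Week 110 shift.

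**Working it through.** No sample size, power or alpha figure is in dispute. The check is of visit days, windows and scope rules.

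**Visit days.** SAP 6.5.2 makes the first dose Day 1, so target day = 7 × week + 1.
- Week 110: 7 × 110 + 1 = 771.
- Week 114: 7 × 114 + 1 = 799.
- Both match SAP Table 1. Nominal gap: 799 − 771 = 28 days.

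**Range of the gap.** The windows come from Protocol Table 1. I assume that the last dose is at the Week 110 visit and that the two windows apply independently.
- Week 110, ±14 days: days 757 to 785.
- Week 114, −7/+14 days: days 792 to 813.
- Shortest gap: 792 − 785 = 7 days. Longest: 813 − 757 = 56 days.

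**Early stoppers.** Protocol 6.3.2 encourages patients who stop study medication to keep attending through Week 114. For illustration, a patient who stops at Week 6 and attends Week 114 has a last value 114 − 6 = 108 weeks after the last dose. The documents give no figure for how many patients would have long gaps.

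**Does an existing rule exclude the Week 114 reading?**
- SAP 6.5.4 limits visits up to Week 110 to on-treatment assessments, but only for efficacy.
- SAP 8.1 defines on treatment as up to 3 days after the last dose, again for efficacy. The shortest gap of 7 days would fall outside it, but the rule does not apply to safety laboratories.
- SAP 10.1.3 defines an on-treatment window for adverse events only. For completers it runs to the first open-label dose. SAP 4.1.2 puts the Week 114 evaluations before that dose, so this window includes Week 114.

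No rule excludes it. Week 114 belongs to the double-blind period and is normally its last reading.

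**Which tables and patients are affected?**
- Affected in 10.4.1 at the final analysis: hematology, serum chemistry, quantitative urinalysis, lipids and the urinalysis positive/negative table, for patients who attend Week 114.
- Not affected in this way: coagulation, which is scheduled at Week 110/EOT but not at Week 114.
- Not in the 10.4.1 categories: NT-proBNP, which Protocol Table 15.2-1 lists under other tests.
- Primary analysis: patients not yet at Week 114 usually contribute an on-treatment last value, so the column then mixes on-drug and off-drug readings.
- Patients who leave the study early may contribute a value on or near treatment.

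**The case against.** The strongest reply is that the SAP states its scope openly and never calls the last value an end-of-treatment value. Paired with the worst value, a last on-study value can legitimately show whether an abnormality persisted or resolved. That is fair, and it is why the existing column should be relabelled and not removed.

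A reader might go further and infer that these tables hide reversible drug effects on potassium, hemoglobin, transaminases or edema. The documents do not support that:
- Worst-value shifts include unscheduled readings.
- CTCAE and edema shifts are given at every scheduled visit, so a Week 110 column stands beside Week 114. It may include some early stoppers already off drug.
- SAP 10.4 summarizes laboratory values and changes by visit.
- SAP 10.4.3 reports liver-test threshold incidences and plots of maximum values.
- SAP 10.1.2 gives hyperkalemia, anemia, hepatic and fluid-retention events separately on study and on treatment.

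Nor do the documents show that the arms converge by Week 114. Resuming RAAS therapy is an instruction that leaves room for alternatives, so it is expected but not certain for each patient.

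A second objection concerns the remedy. Applying the 3-day efficacy rule strictly could discard an EOT sample taken a few days late. The last value would then fall back to an earlier visit, possibly about 12 weeks before, and could miss the abnormality that led to stopping. This stands, and the fix is written to avoid it.

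What the objections do not remove is that the 10.4.1 last-value column, as defined, gives no end-of-treatment status and carries no warning of that.

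**Conclusion.** The point holds for one column. At the final analysis, the 10.4.1 last value for patients seen at Week 114 is taken about 4 weeks off study drug, or 7 to 56 days under the stated assumptions. For early stoppers who remain in follow-up the gap is longer. The column is misleading if read as end-of-treatment status, and 10.4.1 has no by-visit shift to correct that reading.

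The last-value columns in 10.4.2 and 10.6.1 share the definition, but their by-visit shifts largely make up for it, so those two sections need only a label. On-drug changes stay visible in other outputs, so no safety signal is shown to be lost. The change is a cheap improvement to how the tables read and corrects no safety conclusion.

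This rests on attendance at Week 114 with laboratories drawn as scheduled, and on the range assumption that the last dose is at the Week 110 visit.

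**What to change.** - In SAP 10.4.1, add a shift from baseline to the last on-treatment value, defined as the last value up to and including the Week 110/EOT visit. This keeps an EOT sample taken a few days after the last dose. State what applies when no EOT visit took place.
- Keep the existing last on-study value, and label it post-treatment wherever it falls after that visit.
- Apply the same label to the last-value columns in SAP 10.4.2 and 10.6.1.
- Do not reuse the SAP 10.1.3 adverse-event window, because for completers it includes Week 114.

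The cost is a few sentences in the SAP, a flag in the laboratory and edema datasets and one extra column, with no new data. The drawback is that the laboratory on-treatment definition will differ from the adverse-event one, so a footnote should say so.
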